Belimumab and placebo will be supplied as open-label vials and 3rd party unblinding will be employed. The study agent will be reconstituted and diluted by the unblinded site pharmacist or designee, independent of the study (person responsible for receiving and dispensing study agent). Separate monitors will be responsible for the clinical (blinded monitor) and study agent (unblinded monitor) aspects of the study.

If a medical emergency occurs and a decision regarding the subject's condition requires knowledge of the treatment assignment, the study blind may be broken for the specific subject. Whenever possible, the investigator should consult with the principal investigator of the study and data safety monitoring board prior to unblinding any subject. Any broken blind will be clearly justified and explained. The lead site and sponsor must be notified of any broken blind regardless of whether it was done for emergency or non-emergency reasons.

e. Concurrent Medications:

Corticosteroids: Patients that are on glucocorticoids at the time of screening will be required to be on a stable background dose for at least 2 weeks prior to screening (prednisone (or equivalent) dose \leq 15 mg daily).

The prednisone dose will remain stable until week 24 of the study, at which time a taper will be allowed at the discretion of the site investigator and principal investigator.

An increase in the dose of oral prednisone will be permitted, if clinically necessary, during the first 8 weeks after randomization without accounting it as a disease flare. In this case, the dose of prednisone must be tapered (to less than or equal to 25% of the baseline dose) by week 12. However, if the dose of prednisone cannot be tapered by week 12, the event will be considered as disease flare at that time.

Any increase of the prednisone dose after week 8 for IIM disease activity or the use of pulse steroids at any time during the study will be considered a disease flare. An increase of the prednisone dose at any time during the study for an event other than worsening of IIM disease activity will require the patient to return to the baseline dose of prednisone within 10 days, without accounting the event as a disease flare. Patients that are considered treatment failures will be allowed to remain in the study, in respective groups, at the discretion of the treating physician and PI.

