Immunosuppressive agents (IS): Enrolled patients could have had a history of treatment with any of the following IS agents: azathioprine, methotrexate, mycophenolate mofetil, leflunomide,

tacrolimus, cyclosporine, cyclophosphamide, Rituximab, or intravenous gamma globulin [IVIG]. Patients are not required to be on an IS agent at the time of enrollment.

During the enrollment and study period, the only allowed IS agents are: azathioprine, methotrexate, mycophenolate mofetil, tacrolimus, cyclosporine or intravenous gamma globulin [IVIG].

Patients that are on background immunosuppressive (IS) therapy at the time of screening will be required to be on a stable IS agent for \geq 2 months prior to screening (\geq 3 months for IVIG), and on a stable dose of IS agent for \geq 2 weeks prior to screening (except IVIG; no dose change allowed). Dose reduction due to poor tolerance of IS agent will be allowed on a case by case basis.

Therapeutic Agent	Treatment Duration prior to Screening \geq	Dose Increase prior to Screening \geq
Azathioprine	2 months	2 weeks
Methotrexate	2 months	2 weeks
Mycophenolate mofetil	2 months	2 weeks
Tacrolimus	2 months	2 weeks
Cyclosporine	2 months	2 weeks
IVIG	3 months	none

If a dose increase in IS agent or initiation of a new IS agent is clinically necessary during the randomization phase, this will be considered as a disease flare. The patient will be allowed to continue in their respective assigned group at the discretion of the treating physician and PI.

f. Medications and Therapies Prohibited for Concomitant Use:

a. Anti-B-cell therapy:

- i. Wash out of 5 therapeutic half-lives after prior B-cell therapy, or until pharmacodynamic effect would be minimal (e.g., 1 year following Rituximab)
 - IgG levels should be measured monthly in this situation
 - Benlysta should be discontinued in subjects with IgG levels <250 mg/dL associated with a severe or serious infection
- ii. If Rituximab use was medically indicated after the patient's enrolment to the clinical trial, the patient will no longer receive the investigational drug, but enhanced safety monitoring will be required.

b. Intravenous Cyclophosphamide

- i. 180 Days Prior to Belimumab
 - IgG levels should be measured monthly in this situation
 - Benlysta should be discontinued in subjects with IgG levels <250 mg/dL associated with a severe or serious infection

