3. an increased dose of corticosteroid before study week 8 and did not return to $<25\%$ above the baseline dose by week 12.

Endpoints:

1. **Primary Endpoint:**
 - a. Response rate at 40 weeks defined as percentage of patients meeting definition of improvement (DOI) in IIM patients treated with belimumab and standard therapy compared to the percentage of patients meeting DOI treated with placebo and standard therapy.
2. **Secondary Endpoints:**
 - a) Incidence of flares: flare rates during 40 weeks randomization period in patients with IIM treated with belimumab and patients treated with placebo and at week 64 in each group.
 - b) Time to achieve initial improvement defined as the time to reaching DOI.
 - c) Duration of improvement; quantified as the time from achieving improvement to the time of worsening or a disease flare. (Time from 1st DOI to 1st DOW or disease flare event). This will be based on the subset of subjects who achieve improvement.
 - d) Percent change in muscle enzyme levels (CPK and myoglobin) from baseline to week 40 and 64 in each respective group
 1. $<20\%$ reduction: no response
 2. 20-70% reduction: partial response
 3. $>70\%$ reduction: complete response
 - e) Percent change in manual muscle assessment (MMT-8) from baseline to week 40 and week 64 in each respective group.

- 1. <20% reduction: no response
- 2. 20-70% reduction: partial response
- 3. >70% reduction: complete response
- f) Percent change in prednisone dose from baseline to week 40 and week 64 in each respective group
- g) Proportion of subjects, among those on steroids at baseline, able to reduce the prednisone dose to ≤ 5 mg daily at week 40 and week 64 in each respective group.
- h) Flare rate in placebo group during the 40 week randomized treatment phase as compared to that group in the 20 week open label phase.
- i) Serious adverse event and adverse event rates
- j) Changes in B cell populations from baseline to week 40 and week 64
- k) Changes in autoantibody titers from baseline to week 40 and week 64
- l) Changes in immunoglobulin concentrations from baseline to week 40 and week 64

Inclusion Criteria:

Subjects enrolled in the study must meet the following inclusion criteria:

- 1) Adults ≥ 18 years of age
- 2) Have a diagnosis of:
 - a. definite or probable dermatomyositis (DM) by modified Bohan & Peter criteria or

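### The flare rules conflict on three kinds of early treatment change, so one patient can be a flare or not for the secondary flare and duration endpoints

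*Combined protocol and SAP*

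**What the plan says.** **Concurrent Medications (Study Design, part e).** On steroids, "The prednisone dose will remain stable until week 24 of the study". An increase in the first 8 weeks is allowed without counting as a flare, but then "the dose of prednisone must be tapered (to less than or equal to 25% of the baseline dose) by week 12"; if that fails, a flare is recorded at week 12. "Any increase of the prednisone dose after week 8 for IIM disease activity" is a flare, and "the use of pulse steroids at any time during the study will be considered a disease flare". On immunosuppressive agents (IS), where "initiation of a new IS agent is clinically necessary during the randomization phase, this will be considered as a disease flare"; the same sentence covers dose increases. Patients stay in the trial after such events: "Patients that are considered treatment failures will be allowed to remain in the study, in respective groups", and after an IS change "The patient will be allowed to continue in their respective assigned group", in both cases at the physician's and principal investigator's discretion.

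**Definitions, Disease Flare.** Three routes are listed: (1) meeting the definition of worsening (DOW); (2) a steroid or IS started or increased for myositis (IIM) after week 8; (3) a steroid increase before week 8 that has not come back to less than 25% above baseline by week 12. Pulse steroids are not mentioned.

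**Statistical Methods.** Dose adjustments to standard-care drugs are allowed in the first 8 weeks. Steroids and IS are not separated, and nothing is said about whether an adjustment counts as a flare.

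**Endpoints.** The primary endpoint is "Response rate at 40 weeks defined as percentage of patients meeting definition of improvement (DOI". DOI is built from the six core set measures and has no medication term. Flare enters secondary endpoints (a) flare incidence, (c) duration of improvement, and (h) placebo-group flare rate in the randomised versus the open-label phase.

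**The concern.** A flare should follow mechanically from the dosing record. Here a site working from Concurrent Medications and an analyst working from Definitions can code the same patient differently, and nothing says which section governs. With 15 patients per arm, a few such codings could shift the flare comparison, and a choice made after unblinding would be open to challenge. The taper sentence is also an instruction to sites: taken literally, it asks for a steroid cut that the rest of the protocol does not intend.

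A related gap is that the plan expects rescue, keeps rescued patients in their groups, and has no analysis showing how far week-40 response depends on it.

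**Working it through.** **1. Week-12 taper.** For baseline dose B, Concurrent Medications requires at most 0.25 × B; Definitions requires less than 1.25 × B.

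| Baseline | Concurrent Medications | Definitions |
|---|---|---|
| 5 mg | ≤ 1.25 mg | < 6.25 mg |
| 10 mg | ≤ 2.5 mg | < 12.5 mg |
| 15 mg (entry maximum) | ≤ 3.75 mg | < 18.75 mg |

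The limits differ five-fold (1.25/0.25). A patient raised at week 4 and back at exactly 15 mg by week 12 is a flare under the first and not under the second. The first also clashes with its own section: a dose held stable to week 24 cannot be a quarter of baseline at week 12.

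**2. IS change for IIM at week 6, no DOW.** Concurrent Medications covers the whole randomised phase: flare. Definitions route 2 starts after week 8 and route 3 concerns steroids only: no flare.

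**3. Pulse steroids at week 4, back at baseline by week 12, no DOW.** Concurrent Medications: flare. Definitions: route 2 has not started and route 3 is satisfied, so no flare. A pulse for IIM after week 8 is caught by route 2, so the gap is confined to early pulses.

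**4. Endpoints reached.**
- (a) and (h): all three conflicts. For (h) they alter only the randomised-phase side, because the open-label phase lies wholly after week 8.
- (c): mainly conflict 1. Core set measures are first reassessed at week 8, so IS changes and pulses before then precede any recorded DOI. A patient with DOI at week 8 who is back at 15 mg at week 12 has improvement ending after 12 − 8 = 4 weeks under one text and continuing under the other.
- One patient in an arm of 15 is 1/15 = 6.7 percentage points.

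**5. Primary endpoint.** Planned size: 5% vs 50%, two-sided 0.05, 80% power, pooled chi-square, mean rate 0.275:

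n = [1.960 × √(2 × 0.275 × 0.725) + 0.842 × √(0.05 × 0.95 + 0.50 × 0.50)]² / 0.45² = (1.238 + 0.459)² / 0.2025 = 14.2, so 15 per arm.

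This matches the plan; the same formula gives 82.3% power at n = 15. Exact enumeration, using Fisher's test when an expected count is below 5 and chi-square otherwise (my reading of the plan's unspecified choice between them), gives 76.8%. The flare conflicts enter none of these figures.

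One rescued placebo patient counted as a responder could matter. Fisher's p is 0.035 for 1/15 vs 7/15 and 0.109 for 2/15 vs 7/15. Uncorrected chi-square, the test used for sizing, still gives 0.046 for the latter. This shows small-sample fragility to one extra responder from any cause; it does not measure how often rescue would produce one.

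**The case against.** **The taper wording is a slip and the formal definition is usable.** It probably is a slip, given the stable-dose rule beside it. It remains an operative instruction. No simple precedence rule repairs the set either: if Definitions governs, early IS changes and early pulses cease to be flares, against explicit text; if Concurrent Medications governs, or the two lists are combined, the quarter-dose limit comes in.

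**Definitions is silent on pulses, not contrary.** That is fair, and the gap is narrow, but an early pulse can still be coded either way.

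**The 8-week allowance in Statistical Methods does not contradict the IS rule.** This stands. Allowing a change does not say that it is not a flare; the sentence needs clarifying only.

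**The primary endpoint is defined.** This stands too. A reader might infer that response after rescue is left undefined. But DOI has no medication term, the endpoint compares each treatment given with standard therapy, the test is on improvement as defined, the analysis is labelled intention-to-treat, and patients stay in their groups. Together these support DOI regardless of rescue. A per-protocol analysis by actual treatment is also planned, though not defined for rescue.

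**Rituximab or cyclophosphamide rescue has limited reach.** Agreed. These patients stop study drug, and the analysis set requires the first five infusions (weeks 0, 2, 4, 8, 12), so only those starting such rescue after the fifth infusion could count as responders.

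**Conclusion.** The three conflicts are in the current text and need no assumption to show. They bear on secondary endpoints (a) and (h), and on (c) chiefly through the week-12 taper. How many patients they would reclassify is unknown, but each is worth 6.7 points of an arm. The wording should be corrected before unblinding.

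The primary endpoint stands as DOI regardless of rescue; what it lacks is a sensitivity analysis. A reader might infer that the trial loses power through rescue. For illustration, assume that 5% vs 50% are rescue-free rates, that 20% of placebo non-responders are rescued and 20% of those then meet DOI, with rescue on belimumab between one third as common and equally common. Enumerated power falls from 76.8% to 66–69%; with 10% and 10% it is 74–75%. The documents support none of these inputs. If the rates in Sample Size Considerations mean DOI regardless of rescue, as the plan's definition of response suggests, there is no loss against plan. Nor is a false positive the expected direction: rescue that is more common on placebo, or equally common among non-responders, dilutes the difference.

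**What to change.** **Flare rule.**
- Concurrent Medications: change the week-12 target to less than 25% above the baseline dose.
- Disease Flare definition: count any new or increased IS for IIM throughout the randomised phase, keep the week-8 limit for prednisone only, and leave open-label changes covered as now.
- Same definition: add pulse steroids at any time.
- Statistical Methods: state that an IS increase in the first 8 weeks, although permitted, is recorded as a flare.

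**Sensitivity analysis.** State that DOI at week 40 regardless of rescue is primary. Pre-specify one further analysis in which IIM-driven rescue before the week-40 assessment means non-response. Rescue is: pulse steroids at any time; a prednisone increase after week 8 to above baseline; an earlier increase not back to less than 25% above baseline by week 12; or any new or increased IS, including rituximab or cyclophosphamide. DOW alone is not rescue. Nor is a re-increase after the week-24 taper that stays at or below baseline, although it remains a flare.

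**Cost.** Wording only. Prednisone doses and IS changes are already needed for the secondary endpoints, follow-up is unchanged, and the power of the primary test is unaffected. The sensitivity analysis may be weaker, since response can fall in both arms: by the same enumeration its power is 66% at 5% vs 45%, 54% at 5% vs 40%, and 68% at 4.5% vs 45%. It should be read as support for the primary result, not as a second test of it.

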Screening: Once the patient signs the consent form, a screening period of up to two weeks will initiate to determine the patient's eligibility for the study, prior to entering the randomization phase. Only eligible patients will enter the randomization phase.

Randomized Phase: Monthly infusions (of either B or P) will start at week 0 and continue every four weeks until week 36 (10 months) for the “randomized” phase of the study. In addition, there will be a “loading dose” at week 2 (per drug [IND] specifications). The loading dose will consist of either Belimumab or Placebo (saline) in the B or P treatment arms, respectively.

Open Label Phase: Monthly infusions (of B) will start at week 40 and continue every four weeks until week 64 (6 months) for the “open-label” phase of the study.

A comprehensive evaluation of the patient (Physical exam and history, vital signs, AEs, CBC and metabolic panel, GGT, myoglobin, pregnancy test, urinalysis, ESR, CRP, CPK, immunoglobulins, muscle and health evaluations, physician global assessment, patient self-assessments, serum level sampling) will be conducted at weeks 0, 8, 16, 24, 32, 39-40, 52, 64. A less comprehensive set of evaluations (vital signs, AEs, CBC and metabolic panel, GGT, pregnancy test) will be conducted at weeks 2, 4, 12, 20, 28, 36, 40, 44, 48, 56, 60. A detailed schedule of visits and procedures is outlined in appendix A.

A telephone follow-up conversation will also be conducted at weeks 72 and 84.

Optional Exploratory Studies

Blood based biomarker assessments and blood based RNA assessments will be performed on stored samples for consenting patients at Northwell Health only. See Appendix A (schedule of events).

b. Randomization:

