The Biostatistics Unit (BU), within The Feinstein Institute for Medical Research (FIMR), provides state-of-the-art statistical and data management support to the research investigators at Northwell Health, as well as other medical research institutions in the New York area. Its staff of ten PhD and Masters level statisticians and two senior applications programmers has extensive experience in the design, data management, and analysis of hundreds of clinical research

projects, including over 250 clinical trials. Primary expertise is in clinical trials, diagnostic testing and screening, the development of predictive models for prognosis, and development of protocols and grant applications.

Definitions:

All patients are required to meet the Bohan & Peter (1975) diagnostic criteria for definite or probable DM or PM (see Appendix B) and be positive for at least one autoantibody (ANA $\geq 1:80$ or RNP or SSA/SSB or any of the myositis specific autoantibody). Patients with the diagnosis of definite or probable PM will require the presence of at least one myositis specific auto-antibody (antisynthetase autoantibodies (anti-Jo-1, PL-7, PL-12, EJ, OJ), anti-SRP, anti-Mi-2, anti-p140 [also known as anti-MDA5], anti-p155/140 [also known as anti-TIF], anti-NXP-2 [also known as MJ]). Patients with the diagnosis of definite or probable PM in the absence of myositis specific auto-antibodies will require review of the muscle biopsy results and adjudication of the diagnosis by a committee of 3 experts that will be predetermined in advance.

Refractory Myositis: Refractory myositis is defined as chronic IIM with an inadequate response or intolerance to at least three months of corticosteroids and/or an inadequate response or intolerance to at least three months of at least one other immunosuppressive agent (azathioprine, methotrexate, mycophenolate mofetil, leflunomide, cyclophosphamide, tacrolimus, cyclosporine or IVIG).

Core Set Measures (CSM): All enrolled subjects will be required to have active disease based on the clinical core set measures, which is a standard instrument for assessing myositis disease activity. Active disease using the CSM is defined by International Myositis Assessment and Clinical Studies Group ¹¹:

1. Manual muscle testing (MMT-8) with a score $\leq 125/150$

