2. Elevation of at least one muscle enzyme (creatinine kinase [CK]; myoglobin; alanine aminotransferase [ALT]; or aspartate aminotransferase [AST]) to a minimum level of 1.3 times the upper limit of normal.
3. Physician Global Assessment ≥ 2.0 cm using a visual analogue scale (VAS) 10.0 cm in length.
4. Patient Global Assessment ≥ 2.0 cm using a visual analogue scale (VAS) 10.0 cm in length.
5. Global extra muscular disease activity score ≥ 1.0 cm using a visual analogue scale (VAS) 10.0 cm in length. This score is based on the investigator's composite assessment of disease activity of the constitutional, cutaneous, skeletal, gastrointestinal, pulmonary and cardiac scales on the Myositis Disease Activity Assessment Tool (MDAAT).
6. HAQ disability index with a minimum value of 0.25.

The patient will be required to meet an MMT 8 score of $\leq 125/150$ as a major CSM criterion and at least 2 other CSM criteria to classify as an active disease.

In addition, for patients with ≥ 7 years of IIM, muscle biopsy or muscle MRI within 4 months prior to enrollment will be required to document active myositis to avoid enrolling patients with

significant index of damage/ muscle atrophy. This is not applicable to DM patients with a cutaneous VAS score of >3 cm on a 10 cm VAS scale (MDAAT).

Response rate: The response rate will be assessed by the percentage of patients meeting the definition of improvement (DOI). DOI is based on the definition of improvement developed by the International Myositis Assessment and Clinical Studies Group utilizing 6 core set measures.

DOI: DOI is defined as $\geq 20\%$ improvement in any 3 of the CSM, with no more than 2 CSM worsening by $\geq 25\%$ (excluding MMT)¹¹.

Definition of Worsening (DOW): Determination of worsening of the disease activity will be based on the definition of worsening (DOW) criteria developed by the International Myositis Assessment and Clinical Studies Group (IMACS) utilizing 6 core set measures¹¹:

1. worsening of Manual Muscle testing by $\geq 20\%$ and or Physician Global worsening of ≥ 2 cm on a 10 cm VAS or
2. Global extra muscular organ disease activity worsening by ≥ 2 cm on a 10 cm VAS on MDDAT, or
3. 3 of 6 CSM worse by $\geq 30\%$

Disease Flare: IIM Disease Flare is recorded when the patient:

1. reaches DOW;
2. new start or dose increase of corticosteroid or immunosuppressive agent for treatment of IIM after study week 8;

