- c. Testing for latent TB is a standard of care for patients on immunosuppressive therapy and results will be obtained **from their medical record**. If no TB history is found for these patients, a Quantiferon Gold or PPD test will be performed prior to Day 0 as part of **standard of care**.
- d. Hepatitis status will be obtained from patients' **medical records**. If unavailable, testing will be done as part of **standard of care** during the screening period.
- Vital signs will be assessed prior to infusion and after the infusion at every visit.
- Adverse events assessed at every visit. Criteria for grading toxicity will be based on NCI's Common Terminology Criteria for Adverse Events version 4.03. (Adverse Events/Serious Adverse Events (CTCAE Version 4.03)
- A Physical Exam will be performed by the Investigator at Screening, Day 0, Week 8, 16, 24, 32, 40, 52, & 64.
- Urine Pregnancy testing for WOCBP will be conducted at each study visit and 16 weeks after last dose. Urine pregnancy tests must be completed < 7 days prior to the first dose and prior to each IP administration, but not more than once a month. In the event that the urine pregnancy test is indeterminate, a serum pregnancy test will be done.
- Laboratory tests: CBC, Comprehensive metabolic, GGT, ESR, CRP, CPK, myoglobin and urinalysis will be collected at every study visit and follow up week 64.
- An immunoglobulin panel will be collected and assessed at: Screening, Week 40, & 64. Under special circumstances monthly IgG monitoring may be required (see Section: Study Design, part f) and will be performed as part of standard of care.
- Flow Cytometry and RNA-seq are collected at: Day 0, Week 8, 40, Week 48, & Week 60 or 64.
- Cytokine levels (and optional research Northwell only) will be measured at: Day 0, Week 40, & Week 60 or Week 64.
- Patients should be clinically assessed for suicidal ideation and/or behaviour at each study visit using the Columbia Suicide Severity Scale (C-SSRS)
- The Investigator will complete a Physician Global Assessment (PGA, a VAS scale of 10cm), Manual Muscle Test-8 (MMT-8), & Myositis Disease Activity Assessment Tool (MDAAT) at Screening, Day 0, Week 8, 16, 24, 32, 40, 52, & 64
- The Investigator will complete a Muscle Damage Index (MDI) assessment at Screening, Week 40 and Week 64
- Health Assessment Questionnaire (HAQ) and Patient Global Assessment (PGA, a VAS scale of 10cm) will be completed by subjects at Screening, Day 0, Week 8, 16, 24, 32, 40, 52, & 64

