The Biostatistics Randomization Management System (BRMS) is a secure, HIPAA-compliant, web-based application that allows investigators to randomize subjects into randomized clinical trials (RCTs) using their personal computer. The BRMS allows for multi-center, stratified, and single/double blinded RCTs, using permuted blocks. Randomization notifications are automatically sent to the PI and other authorized personnel. Using BRMS is a good way to maintain compliance in RCTs.

Statistical Considerations

SPECIFIC STATISTICAL AIMS

The primary objective of the study is to compare subjects in the Belimumab group and subjects in the placebo group with respect to response (improvement) at week 40.

The specific aims of the study are to compare the two treatment arms (Belimumab vs. Placebo [P vs. B]), during the 40-week randomized phase of the study, with respect to the following:

1. Response at week 40.
2. Flare rates during the 40-week treatment period.
3. Time-to-achieve (initial) improvement during the 40-week randomized phase of the study
4. Duration of improvement during the 40-week randomized phase of the study, among those who achieved improvement (this is essentially a time-to-flare/relapse analysis from the time that you achieved improvement)
5. Change in muscle enzyme levels (CPK, myoglobin) from baseline to week 40
6. Change in MMT-8 from baseline to week 40
7. Change in prednisone dose from baseline to week 40

8. Proportion of subjects able to reduce prednisone dose to ≤ 5 mg at week 40
9. Change in B cell populations, immunoglobulin levels and BLys levels from baseline to week 40.
10. Change in autoantibody titers from baseline to week 40.
11. Rates of SAEs and AEs experienced

STATISTICAL METHODS

All subjects will be analyzed according to the intention-to-treat [ITT] principle. A subject will be considered evaluable and will be included in the intention-to-treat analysis if he/she received at least the first five of the planned infusions during the randomized phase of the study. Subjects who do not get the first five infusions will be considered ‘drop-outs’. It should be noted that the study protocol calls for patients remaining on their treatment assignment. However, adjustments in dosages of medications used in their ‘standard care’ are permitted during the first 8 weeks. Analyses that take into account the actual treatment received (e.g. accounting for compliance, etc.) will be carried out as a secondary analysis (per protocol [PP] analysis).

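### Secondary endpoint e) grades a fall in MMT-8 of 20% or more as a response and every gain in strength as no response

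*Combined protocol and SAP*

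**What the plan says.** In the combined protocol and SAP, under Endpoints, secondary endpoint d) grades percent change in CPK and myoglobin by the size of the reduction: below 20% is no response, 20 to 70% partial, above 70% complete. Secondary endpoint e), "Percent change in manual muscle assessment (MMT-8) from baseline to week 40 and week 64 in each respective group", is followed by the same three lines, ending with ">70\%$ reduction: complete response".

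The direction of each measure is set under Definitions, Core Set Measures (CSM). Active disease means an enzyme at 1.3 or more times the upper limit of normal, and "Manual muscle testing (MMT-8) with a score" of 125/150 or less. High enzymes and low muscle scores are therefore the signs of disease.

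Two other definitions also use muscle testing:

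- The definition of improvement (DOI) asks for at least 20% "improvement in any 3 of the CSM, with no more than 2 CSM worsening by" 25% or more, and muscle testing may not be among the worsened measures.
- The Definition of Worsening (DOW) includes "worsening of Manual Muscle testing by" 20% or more. Reaching DOW is recorded as a disease flare.

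Under Statistical Considerations, aim 6 is "Change in MMT-8 from baseline to week 40". Statistical Methods item 5 analyses it with a mixed model and covers both continuous and categorical outcomes. If the model is not feasible, the fallback compares percent change, glossed as reductions, in enzymes, MMT-8 and prednisone dose together. A chi-square or Fisher test on grouped values is allowed as an option, with CPK as the example.

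**The concern.** The grades suit a measure that falls with recovery. Applied to one that rises with recovery, they reverse the meaning of the endpoint. Nothing in the documents reverses the direction for MMT-8 or defines the reduction on another scale, such as the distance from a full score.

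If the grades are tabulated as written, lost strength is reported as efficacy. Full recovery is pooled with no change and with losses below 20%. One patient could be a partial responder on e) and, through DOW, a flare on secondary endpoint a). If the problem is found only after unblinding, replacement grades would have to be chosen with the results in view.

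**Working it through.** The plan gives no numerical result for MMT-8 grades and no expected distribution of change, so there is no figure to reproduce. The check applies the written grades to the scale.

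**Inputs.** Cut-offs of 20% and 70% (endpoint e); maximum score 150 and active-disease limit 125 (Core Set Measures); 20% improvement (DOI); 20% worsening (DOW). All percentages are taken relative to the baseline score. This is an assumption, because DOI and DOW do not state their denominator.

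**Step 1: grades as written.** Reduction = (baseline − score) / baseline.

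| Baseline | Score | Reduction | Grade under e) |
|---|---|---|---|
| 125 | 150 | −25/125 = −20.0% | no response |
| 125 | 101 | 24/125 = 19.2% | no response |
| 125 | 100 | 25/125 = 20.0% | partial |
| 125 | 38 | 87/125 = 69.6% | partial |
| 125 | 37 | 88/125 = 70.4% | complete |
| 100 | 150 | −50/100 = −50.0% | no response |
| 100 | 81 | 19/100 = 19.0% | no response |
| 100 | 80 | 20/100 = 20.0% | partial |
| 100 | 30 | 70/100 = 70.0% | partial |
| 100 | 29 | 71/100 = 71.0% | complete |

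With whole-number scores, a patient starting at 125 is graded no response at 101 to 150, partial at 38 to 100 and complete at 37 or less. From 100 the bands are 81 to 150, 30 to 80, and 29 or less.

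**Step 2: against DOW and DOI.** A response under e) is a reduction of at least 20%. On the same denominator and baseline, this is the muscle-testing element of DOW. The fall from 125 to 100 satisfies both. If the *and or* in DOW item 1 is read as *or*, that fall alone reaches DOW and is recorded as a flare. Conversely, a rise of 20% or more, which counts as an improved measure for DOI, has a negative reduction and is always graded no response.

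**Step 3: reversing the sign only.** Largest possible rise = (150 − baseline) / baseline.

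- Baseline 125: 25/125 = 20.0%, reached only at a full score.
- Baseline 110: 40/110 = 36.4%.
- Baseline 100: 50/100 = 50.0%.
- Baseline 89: 61/89 = 68.5%.
- Baseline 88: 62/88 = 70.5%.

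A rise of 20% needs a baseline of 150/1.2 = 125 or less. A rise above 70% needs one below 150/1.7 = 88.2. Full recovery from 100 would then be only partial. Inclusion criterion 6 admits dermatomyositis patients who do not meet the muscle-testing criterion. Those entering above 125 could never be graded responders.

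**Step 4: percent of the deficit (150 − score).** From 125, a score of 130 is 5/25 = 20% of the deficit but 5/125 = 4.0% of the score. A score of 149 is 24/25 = 96% of the deficit but 24/125 = 19.2% of the score. Used in e) alone, this scale would disagree with a DOI based on percent of score.

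**The case against.** The strongest reply is that little depends on these grades. Aim 6 names change in MMT-8 without categories, a mixed model is planned, and the grouped test is optional with CPK as its example. Nothing in Statistical Methods requires the grades under e) to be tabulated. This stands and limits the weight of the point. It does not remove it: the grades are part of a listed endpoint, item 5 admits categorical outcomes and grouping by categories set in advance, and the only ones set for MMT-8 are the reversed ones. The reductions label in the fallback is a lesser matter: for MMT-8 it gets the sign wrong but does not alter a two-sided comparison.

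A second reply is that improvement was plainly meant and a change of word would do. Improvement probably was meant, and the change would cure the direction. The ceiling is then a caution about the replacement, not part of the error: everyone meeting the 125 limit could reach a 20% rise, and a percent-of-score DOI has the same ceiling. But full recovery from 100 would still be only partial, so the sponsor has to choose a definition.

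A third reply concerns week 64. Item 5 gives its time levels as baseline and 40 weeks, but also allows data from every visit in the treatment-by-time interaction. Week 64 is therefore not wholly outside the methods text. The stated aims, however, are confined to the 40-week randomized phase. This is a side issue and does not bear on the direction error.

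**Conclusion.** The concern holds. Endpoint e) as written grades loss of strength as response and every gain as no response. That conclusion needs only the plan's own rule that a low MMT-8 marks active disease. The exact overlap with DOW also needs percent of the score, and the same baseline, in both rules.

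The consequence is confined to one of the twelve secondary endpoints (a to l), and there to the graded form. The primary DOI endpoint and the sample size are unaffected, and continuous change in MMT-8 can still be read correctly from its sign. The number of patients who would be misgraded cannot be estimated from the documents. The point should be fixed, but it does not threaten the trial's main conclusion.

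**What to change.** 1. Delete the three reduction grades under e) and state the direction, for example: *Percent change in MMT-8 from baseline to weeks 40 and 64, by arm; an increase is improvement.*
2. In Statistical Methods item 5, take MMT-8 out of the wording that describes percent change as reductions.
3. Report MMT-8 as continuous change, using the planned mixed model at week 40. For week 64, add a sentence giving a descriptive summary by arm or naming the model. The aims stop at week 40, and under the open-label plan ("Monthly infusions (of B) will start at week 40 and continue every four weeks until week 64") both arms receive belimumab by then, so week 64 is not a placebo comparison.
4. If a graded summary is wanted, define it before unblinding, with improvement as a rise and cut-offs reachable below the 150 ceiling. Name the baseline visit, because the schedule has "Manual Muscle Test-8 (MMT-8), & Myositis Disease Activity Assessment Tool (MDAAT) at Screening, Day 0, Week 8" and later visits, which gives two candidates. State one denominator for MMT-8 in e), DOI and DOW. Percent reduction of the deficit is one option, provided its disagreement with a percent-of-score DOI is resolved.

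Items 1 and 2 are the minimum. The cost is a few lines of endpoint and analysis text, with no new data, visits or patients.
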